12.3 Data Management and Processing

12.3.1 Study Documentation

Study documentation includes but is not limited to source documents, case report forms, monitoring logs, appointment schedules, study team correspondence with sponsors or regulatory

bodies/committees, and regulatory documents that can be found in the DCI-mandated “Regulatory Binder,” which includes but is not limited to signed protocol and amendments, approved informed consent forms, FDA Form 1572, and CAP and CLIA laboratory certifications.

Source documents are original records that contain source data, which is all information in original records of clinical findings, observations, or other activities in a clinical trial necessary for the reconstruction and evaluation of the trial. Source documents include but are not limited to hospital records, clinical and office charts, laboratory notes, memoranda, subjects' logs or evaluation checklists, pharmacy dispensing records, recorded data from automated instruments, copies or transcriptions certified after verification as being accurate copies, microfiches, photographic negatives, microfilm or magnetic media, x-rays, subject files, and records kept at the pharmacy, at the laboratories and at medico-technical departments involved in the clinical trial. When possible, the original record should be retained as the source document. However, a photocopy is acceptable provided that it is a clear, legible, and an exact duplication of the original document.

12.3.2 Primary Data Collection Document

The Excel spreadsheet will be the primary data collection document for the study. The spreadsheet will be updated in a timely manner following acquisition of new source data. Only the PI, the study coordinator, the data management team, and the clinical trials manager are permitted to make entries, changes, or corrections in the spreadsheet.

12.3.3 Data Management Procedures and Data Verification

Users of the Excel spreadsheet will have access based on their specific roles in the protocol, i.e. the PI, the study coordinator, the data management team, and the clinical trials manager.

The data management team and the statistical team will cross-reference the data to verify accuracy. Missing or implausible data will be highlighted for the PI requiring appropriate responses (i.e. confirmation of data, correction of data, completion or confirmation that data is not available, etc.).

The spreadsheet will be reviewed and discussed prior to spreadsheet closure, and will be closed only after resolution of all remaining queries. A record will be kept of all subsequent changes to the data.

12.3.4 Coding

All medical terms will be coded using CTCAE v.4.0, which has been harmonized to MedDRA (Medical Dictionary for Regulatory Activities) coding. Medication will be coded according to the World Health Organization Drug Dictionary.

12.3.5 Study Closure

Following completion of the studies, the PI will be responsible for ensuring the following activities:

- Data clarification and/or resolution
- Accounting, reconciliation, and destruction/return of used and unused study drugs
- Review of site study records for completeness
- Shipment of all remaining laboratory samples to the designated laboratories

13 STATISTICAL METHODS AND DATA ANALYSIS

All statistical analysis will be performed under the direction of the statistician designated in key personnel. Any data analysis carried out independently by the investigator must be approved by the statistician before publication or presentation.

13.1 Analysis Sets

As indicated in section 7.4, subject to the availability of data, all patients who receive perampanel treatment will be included in safety analyses. All patients who complete the treatment period of the study will be included in efficacy analyses.

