3.2 Design and Procedure

This is a Phase 4 single-arm study to assess the efficacy of perampanel as an adjunct anti-epileptic in patients with primary glioma that are presenting refractory partial onset seizure activity (defined as 3 or more seizures in a 28-day period). In this study, patients will be started on a dose of 2 mg of perampanel daily taken orally at bedtime for 2 weeks. At the start of week 3 Perampanel will be titrated up in dose in 2mg increments per week up to 8mg daily, as long as it is well tolerated by the patient. The highest dose of perampanel will be 8 mg orally at bedtime. Patients will begin the treatment period of the study starting at week 5 and will continue through the end of week 12. The planned treatment dose is 8mg, but the dose can be modified by the physician based on patient reported tolerability. Patients will be assessed in the Brain Tumor Center Clinic every 8 weeks. Study assessments will be made at enrollment, 8 weeks, 16 weeks, and 24 weeks.

Assessments will include history and physical examination (H&P) including Karnofsky Performance Status (KPS), neurological examination, evaluation of seizure history, patient-reported outcomes of QoL, and neurocognitive testing using CNS Vital Signs®. After a total of 16 weeks of therapy, perampanel will be tapered for 3 weeks and then will be discontinued, such that at week 20, patients will only be taking their original AED regimen. Patients will then be monitored through Week 24. Patients will remain on their original AED therapy during this treatment time and the dose of their original AED regimen at the start of the study will not be changed while they are on study. If seizure control is achieved during the treatment period or if seizures occur during the tapering period, patients can be continued on perampanel per the discretion of the treating physician. In this instance, perampanel will be prescribed by the treating physician and not provided within the confines of the study. Efficacy will be assessed using a log of patient-reported seizure activity. As is standard procedure at the PRTBTC, patients will be given a log to record the number of seizures that occur. Research team members will regularly contact patients for reminders and reports from the log. Safety will be assessed with the following laboratory evaluations: complete blood count (CBC) with differential, complete metabolic panel (CMP), and toxicity assessment.

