5.2.2 Clinical experience

Perampanel is currently FDA-approved for the adjunctive treatment of refractory partial seizures in patient \geq 12 years of age. In a pooled analysis of three phase III studies involving 1,478 patients, median change in partial seizure frequency was greater with perampanel in comparison to placebo.² Specifically, median change in partial seizure frequencies was as follows: perampanel 4 mg, -23.3%; perampanel 8 mg, -28.8%; perampanel 12 mg, -27.2%; and placebo, -12.8%. Moreover, 50% responder rates were as follows: perampanel 4 mg, 28.5%; perampanel 8 mg, 35.3%; perampanel 12 mg, 35.0%; and placebo, 19.0%. In this pooled analysis, perampanel was well tolerated with the most frequent treatment-emergent adverse events (TEAEs) being dizziness, somnolence, and headache. Of note, there were no deaths reported and no clinically meaningful mean change in laboratory values, electrocardiography (ECG) findings, or vital signs.¹⁰ TEAEs from the pooled analysis are listed in the table below for perampanel dose 2 mg to 12 mg and placebo.

Adverse Event, n (%)	Placebo (n=442)	Perampanel 2 mg (n=180)	Perampanel 4 mg (n=172)	Perampanel 8 mg (n=431)	Perampanel 12 mg (n=255)
Any TEAE	294 (66.5)	111 (61.7)	111 (64.5)	350 (81.2)	227 (89.0)
Dizziness	40 (9.0)	18 (10.0)	28 (16.3)	137 (31.8)	109 (42.7)
Somnolence	32 (7.2)	22 (12.2)	16 (9.3)	67 (15.5)	45 (17.6)
Headache	50 (11.3)	16 (8.9)	19 (11.0)	49 (11.4)	34 (13.3)
Fatigue	21 (4.8)	8 (4.4)	13 (7.6)	36 (8.4)	31 (12.2)
Irritability	13 (2.9)	7 (3.9)	7 (4.1)	29 (6.7)	30 (11.8)
Nausea	20 (4.5)	4 (2.2)	5 (2.9)	25 (5.8)	20 (7.8)
Fall	15 (3.4)	2 (1.1)	3 (1.7)	22 (5.1)	26 (10.2)
Nasopharyngitis	18 (4.1)	7 (3.9)	9 (5.2)	23 (5.3)	11 (4.3)
Upper respiratory	12 (2.7)	11 (6.1)	6 (3.5)	14 (3.2)	10 (3.9)

tract infection					
Ataxia	0 (0.0)	0 (0.0)	1 (0.6)	14 (3.2)	21 (8.2)
Balance disorder	2 (0.5)	0 (0.0)	0 (0.0)	22 (5.1)	8 (3.1)

Most TEAEs were mild to moderate and appeared to be dose related. From the pooled analyses, discontinuation of perampanel at 4 mg was 2.9%, at 8 mg was 7.7%, and at 12 mg was 19.2% in comparison to placebo.¹⁰ Common discontinuation TEAEs were dizziness, convulsion, and somnolence.

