Perampanel will be given according to FDA-approved guidelines over a 24-week period. Patients will be started on a dose of 2 mg daily taken orally at bedtime for 2 weeks. At the start of week 3 Perampanel will be titrated up in dose in 2mg increments per week up to 8mg daily, as long as it is well tolerated by the patient. Weeks 1 and 2, patients will take 2mg, Week 3 they will take 4 mg, Week 4 they will take 6mg and starting at week 5 they will take 8mg. Highest dose will be 8 mg orally at bedtime. Starting at week 5, patients will begin the treatment period, which goes from day 1 of Week 5 through day 7 of Week 16. Patients will be assessed in the Brain Tumor Center Clinic every 8 weeks. Assessments will be made at enrollment, 8 weeks, 16 weeks, and 24 weeks. Assessments will include history, physical examination, neurological examination, evaluation of seizure history, patient-reported outcomes of quality of life, and neurocognitive testing using CNS Vital Signs®. After a total of 16 weeks on therapy, perampanel will be tapered down. At Week 17, patients will begin taking 6mg of perampanel, Week 18 4mg, Week 19 2mg, and Week 20 they will no longer take perampanel. Patients will be considered off treatment at the end of week 20, once perampanel has cleared their system. The planned treatment dose is 8mg, but the dose can be modified by the physician based on patient reported tolerability. Titration and taper periods will be determined by the physician in the case where patients do not reach the planned treatment dose of 8 mg daily. Patients will continue to take their original AED regimen after they stop perampanel. Patients will then be monitored through Week 24. Patients will remain on their original AED regimen during this treatment time and the dose of their original AED at the start of the study will not be changed while they are on study. If seizure control is achieved during the treatment period or if seizures occur during the tapering period, patients can be continued on perampanel per the discretion of the treating physician. In this instance, perampanel will be prescribed by the treating physician and not provided within the confines of the study. As is standard procedure at the PRTBTC, patients will be given a log to record the number of seizures that occur. Research team members will regularly contact patients for reminders and reports from the log.

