7.4 Definition of Evaluable Subjects, On Study, and End of Study

All patients who complete the treatment period will be included in the primary endpoint analysis. All patients who received protocol treatment, regardless of duration, will be included in the safety analysis.

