10.7 Early Withdrawal of Subject(s)

10.7.1 Criteria for Early Withdrawal

Subjects may voluntarily withdraw from the study at any time. The PI may also withdraw a subject from the study at any time based on his/her discretion. Reasons for PI-initiated withdrawal may include, but is not limited to the following:

- Pregnancy
- Upon request of the subject
- If, in the investigator's medical judgment, further participation would be injurious to the subject's health or wellbeing
- Development of intolerable symptoms
- Non-compliance of the subject
- Development of any exclusion criteria

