13.4.1 Variable

Efficacy will be assessed by the 50% responder rate, defined as the percentage of patients with a $\geq 50\%$ seizure reduction during the treatment period compared with the seizure frequency before initiation of perampanel. Seizure frequency during treatment perampanel will be computed as the ratio of the total number of seizure episodes while receiving perampanel during the treatment period and the number of days perampanel is administered.

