13.8 Sample Size Calculation

The one-arm study will assess the efficacy of perampanel for the treatment of primary brain tumor patients with partial onset seizures. The basis for this assessment is the percentage of patients with a $\geq 50\%$ seizure reduction during the treatment period compared with the seizure frequency before initiation of perampanel (i.e. 50% responder rate).

Several recently conducted randomized studies of patients with partial-onset seizures have reported a 50% responder rate of approximately 20% within the standard treatment arm.²⁻⁴ Steinhoff (2009) also reports a 50% responder rate of approximately 35% within a general population of patients with partial-onset seizures treated with perampanel.²

This study has been designed with 90% power to detect an increase in the 50% responder rate during the treatment period from a benchmark of 20% to 35%. Assuming a type I error rate of 0.1, 61 patients will be required. Based on prior studies the early discontinuation rate was 16%, therefore 71 patients will be enrolled to compensate for patients discontinuing prior to the completion of the treatment period.

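### The primary analysis uses only patients who complete treatment, with no all-treated analysis, so the single-arm test against 20% is biased towards success if non-completers respond less often

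*Combined protocol and SAP*

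**What the plan says.** Section 7.4 states: "All patients who complete the treatment period will be included in the primary endpoint analysis". Section 13.1 extends this to efficacy generally: "All patients who complete the treatment period of the study will be included in efficacy analyses". Both sections contrast this set with the safety set, which takes everyone who received perampanel. The word only does not appear, but the sample-size text in Sections 3.5 and 13.8 leaves no other reading, because enrolment is raised from 61 to 71 to replace patients who stop early: "Based on prior studies the early discontinuation rate was 16%, therefore 71 patients will be enrolled".

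Section 13.4.2 tests the responder rate with a one-sample binomial test against a fixed 20% at the 0.1 level. Section 13 contains no all-treated efficacy analysis, no sensitivity analysis and no rule for classifying a patient who stops early. The further seizure-frequency analysis in Section 13.4.2 is descriptive and falls under the same efficacy set.

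The documents disagree on when the treatment period ends. Section 3.2: "Patients will begin the treatment period of the study starting at week 5 and will continue through the end of week 12". Section 7.1: "patients will begin the treatment period, which goes from day 1 of Week 5 through day 7 of Week 16".

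**The concern.** Completing the treatment period happens after treatment starts and can depend on how the patient fares. On earlier experience with the drug, Section 5.2.2 reports: "Common discontinuation TEAEs were dizziness, convulsion, and somnolence". Section 10.7.1 lists "Development of intolerable symptoms" and non-compliance among the reasons for withdrawal, and Section 7.1.1 removes patients who miss more than three doses. If those who leave respond less often than those who stay, the completer rate overstates the rate among everyone treated. A randomised trial would apply the same exclusion to its control arm. Here the comparator is a fixed number, so nothing offsets the selection.

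At stake is a declaration of efficacy when the rate in all treated patients is no better than the benchmark. The objective in Sections 3.1 and 6 concerns patients with glioma and refractory seizures and is not restricted to those who complete treatment.

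An explicit counting rule is needed in any case. Section 13.4.1 builds on-treatment seizure frequency from "the total number of seizure episodes while receiving perampanel during the treatment period and the number of days perampanel is administered". A patient who stops in Weeks 1 to 4, before the treatment period begins, therefore has no defined response.

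**Working it through.** **Inputs from the documents.** Null rate 0.20, target rate 0.35, level 0.10 and power 90% (Sections 13.4.2 and 13.8); 61 evaluable patients, 71 enrolled, 16% early discontinuation (Section 13.8); 7.7% discontinuation at 8 mg (Section 5.2.2).

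**Assumptions.** The test is exact and one-sided (the plan does not state sidedness). All 71 enrolled patients are treated. The ratio *r* of the non-completer to the completer response rate is not in the documents and is varied from 1 to 0.

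**Reproducing the plan.** With an exact one-sided test, the smallest n with at least 90% power is 61. Success needs 17 or more responders, with P(X ≥ 17 | 61, 0.20) = 0.088 and P(X ≥ 17 | 61, 0.35) = 0.905. Putting 0.05 in each tail would need 77, so the one-sided reading fits the plan. For enrolment, 61 × 1.16 = 70.8, which gives 71.

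**Chance of success when the all-treated rate is exactly 20%.** Let completers ~ Bin(71, 0.84), with mean 71 × 0.84 = 59.6. Fixing the all-treated rate at 0.20 gives

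completer rate = 0.20 / (0.84 + 0.16 *r*).

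The exact test is applied to each possible number of completers and the results are averaged:

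| *r* | Completer rate | Chance of success |
|---|---|---|
| 1 | 0.200 | 0.078 |
| 0.79 | 0.207 | 0.100 |
| 0.75 | 0.208 | 0.105 |
| 0.5 | 0.217 | 0.141 |
| 0.25 | 0.227 | 0.187 |
| 0 | 0.238 | 0.246 |

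The nominal 10% is passed once *r* falls below about 0.79.

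**An intermediate case.** Suppose 7.7 of the 16 percentage points are treatment failures and the other non-completers respond like completers. The completer rate is then 0.20 / (1 − 0.077) = 0.217 and the chance of success is 0.138. Treating the 7.7% as failures is an assumption; Section 5.2.2 does not say so.

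**How a single result can flip.** With 60 completers, 17 responders pass: P(X ≥ 17 | 60, 0.20) = 0.077. Counted over 71 treated, the same 17 give P(X ≥ 17 | 71, 0.20) = 0.243. At 71 treated, 19 responders are not enough (0.104), and 20 are needed (0.062).

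**Power of the all-treated analysis** (71 treated, success at 20 or more):

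| Assumption | All-treated rate | Power |
|---|---|---|
| 35% in all treated | 0.350 | 0.910 |
| 35% in completers, half that in non-completers | 0.35 × (0.84 + 0.08) = 0.322 | 0.802 |
| 35% in completers, none in non-completers | 0.35 × 0.84 = 0.294 | 0.634 |

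In the last case the completer test, averaged over the number of completers, has power 0.886. In 25% of such trials completers succeed while the all-treated analysis does not. The first n with 90% power at 0.294 is 141.

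**If the benchmark itself left out dropouts.** The matching all-treated rate is 0.20 × 0.84 = 0.168, and P(X ≥ 20 | 71, 0.168) = 0.011. Counting non-completers as non-responders against 20% would then be conservative.

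**The case against.** The strongest reply is that the direction and size of the bias rest on a response rate the documents do not give. If non-completers respond at 0.79 of the completer rate or better, the level does not exceed the nominal 10%, and the 25% figure requires no response at all in any of them. The plausibility evidence is mixed: dizziness, somnolence and intolerable symptoms are tolerability events, and a patient who stops for somnolence may be a seizure responder. Only convulsion points to lack of efficacy. It comes without a frequency, and the data are from general epilepsy rather than glioma. The denominator behind the 20% is also unstated. If the benchmark left out dropouts, completers are the matched comparison. Finally, the trials in which the two analyses disagree when 35% holds in completers are not false successes, because 29.4% does exceed 20%.

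These limits stand, and they are why the bias is stated conditionally and over a range. They do not remove the gap. The plan reports only the set that is more favourable if non-completers do worse, and it has nothing to show whether they do. Uncertainty about the benchmark is a reason to report both sets. The loss of power is a real argument against making the all-treated analysis primary. It is a weaker argument against a supporting analysis that leaves the completer test intact and decides only whether the claim extends to all treated patients. The threshold of 20 applies only if 71 are treated and must be recalculated otherwise.

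**Conclusion.** The concern holds and should be fixed. The completers-only set and the absence of any all-treated efficacy analysis are clear from the text. The bias towards success is conditional on non-completers responding less often than completers. At 16% non-completion and a true all-treated rate of 20%, the chance of declaring success runs from 8% (equal response) through 14% (half) to 25% (none, the extreme case), against a nominal 10%. These figures assume an exact one-sided test, 71 treated, and a 20% benchmark that refers to all treated patients, which the documents do not establish. The conflict over Week 12 or Week 16 is a separate inconsistency, but it leaves membership of the primary set undefined.

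**What to change.** In Sections 7.4 and 13.1, pre-specify an efficacy analysis of all patients who took at least one dose. Anyone who stops before the end of the treatment period, including during titration or under Section 7.1.1, counts as a non-responder. In Section 13.4.2, state the success threshold for the number actually treated: at 71 treated it is 20 responders, exact level 0.062.

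At minimum, require this analysis to support the conclusion before efficacy is claimed in all treated patients, and otherwise limit the claim to completers. State that the 90% power applies to completers and that the benchmark's handling of dropouts is unknown. Reconcile Sections 3.2 and 7.1 on the end of the treatment period so that a completer is defined.

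As a supporting analysis this costs wording in Sections 7.4, 13.1 and 13.4.2 plus one table, with no new data. The price is that the wider claim has 63% power at 71 if 35% holds only in completers and non-completers do not respond. Making the all-treated analysis primary with 90% power in that case would need about 141 patients. That would be a redesign, and it is optional.

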13.2 Patient Demographics and Other Baseline Characteristics

Socio-demographic and clinical characteristics of patients receiving perampanel treatment on this study will be summarized. For categorical variables, frequencies and percentages will be provided. Means with standard deviations or medians/percentiles will summarize non-categorical variables.

13.3 Treatments

The total number of days that the patient received perampanel treatment will be determined for each patient. The percentage of patients who had dose modifications not consistent with the planned dosing during titration, treatment, and tapering will be tabulated by dosing period (i.e. titration, treatment, and tapering).

13.4 Primary Objective

The primary objective of this study is to assess the efficacy of perampanel as an adjunct AED to levetiracetam in patients with primary glioma presenting refractory partial onset seizure activity.

13.4.1 Variable

Efficacy will be assessed by the 50% responder rate, defined as the percentage of patients with a $\geq 50\%$ seizure reduction during the treatment period compared with the seizure frequency before initiation of perampanel. Seizure frequency during treatment perampanel will be computed as the ratio of the total number of seizure episodes while receiving perampanel during the treatment period and the number of days perampanel is administered.

